APPENDIX 2. PARTIAL DATE CONVENTIONS

Imputed dates will NOT be presented in the listings.

ALGORITHM FOR PROSTATE CANCER HISTORY

Partial date to be imputed as:

Start date	Earliest possible date	first day of month if day unknown or 1 st January if day and month are unknown
Stop date	Latest possible date	last day of month if day unknown or 31 st December if day and month are unknown

ALGORITHM FOR PRIOR / ACTIVE PROCEDURES, RADIOTHERAPIES, CANCER THERAPIES AND MEDICATIONS

Partial date to be imputed as:

Start date	Earliest possible date	first day of month if day unknown or 1 st January if day and month are unknown
Stop date	Latest possible date	last day of month if day unknown or 31 st December if day and month are unknown

General rules:

[figure not shown]
- If start date \leq study med start date, assign as prior
- If stop date \geq study med start date, assign as concomitant

If Missing Stop date: (Rules 2)

- If stop date is missing, assign as prior and concomitant

If Missing Start date: (Rules 3)

- If stop date $<$ study med start date, assign as prior
- If stop date \geq study med start date, assign as prior and concomitant

Document: K:\AAA\Ga-PSMA-R2\VYA27826\ Biostatistics\Documentation\SAP\v2.0\Ga-PSMA-R2-SAP_v2.0
 Author:  Version Number: 2.0

Version Date: 29JUN2020

Template No.: CS_TP_BS016 Revision 5
 Effective Date: 01Apr2018

Reference: CS_WI_BS005

Statistical Analysis Plan

START DATE	STOP DATE	ACTION
Known	Known	General rules
	Partial	General rules
	Missing	General rules
Partial	Known	General rules
	Partial	General rules
	Missing	Rules 2
Missing	Known	Rules 3
	Partial	Rules 3
	Missing	Rules 2

ALGORITHM FOR TREATMENT EMERGENT OF ADVERSE EVENTS

START DATE	STOP DATE	ACTION
Known	Known	If start date < study med start date or start date > actual date of last follow up visit, then not TEAE If start date >= study med start date and start date <= actual date of last follow up visit, then TEAE
	Partial	
	Missing	
Partial, but known components show that it cannot be on or after study med start date	Known	Not TEAE
	Partial	
	Missing	
Partial, could be on or after study med start date	Known	Impute start date as earliest possible date, (i.e. first day of month if day unknown or 1st January if day and month are unknown), except if only day is missing and month and year of start date are the same as for study med start date or if day and month are missing and year of start date is the same as for study med start date. In the latter cases, the study med start date will be used for the imputation. If start date <= stop date, then: If stop date < study med start date, then not TEAE If start date > actual date of last follow up visit, then not TEAE

Document: K:\AAA\Ga-PSMA-R2\VYA27826\ Biostatistics\Documentation\SAP\v2.0\Ga-PSMA-R2-SAP_v2.0
 Author: [Redacted] Version Number: 2.0

Version Date: 29JUN2020

Template No.: CS_TP_BS016 Revision 5
 Effective Date: 01Apr2018

Reference: CS_WI_BS005

START DATE	STOP DATE	ACTION
		If stop date \geq study med start date and start date \leq actual date of last follow up visit, then TEAE If start date $>$ stop date, then: Consider the start date as Missing and apply the algorithms for missing start date
	Partial	Impute start date as above. Impute stop date as latest possible date (i.e. last day of month if day unknown or 31 st December if day and month are unknown), if not resulting in a date later than the date of patient's death. In the later case the date of death will be used for imputation. If start date \leq stop date, then: If stop date $<$ study med start date, then not TEAE If start date $>$ actual date of last follow up visit, then not TEAE If stop date \geq study med start date and start date \leq actual date of last follow up visit, then TEAE If start date $>$ stop date, then: Consider the start and stop dates as Missing and apply the algorithms for missing start date
	Missing	Assumed TEAE
Missing	Known	If stop date $<$ study med start date, then not TEAE If stop date \geq study med start date, then TEAE
	Partial	Impute stop date as latest possible date (i.e. last day of month if day unknown or 31 st December if day and month are unknown), if not resulting in a date later than the date of patient's death. In the later case the date of death will be used for imputation: If stop date $<$ study med start date, then not TEAE If stop date \geq study med start date, then TEAE
	Missing	Assumed TEAE

Document: K:\AAA\Ga-PSMA-R2\VYA27826\ Biostatistics\Documentation\SAP\v2.0\Ga-PSMA-R2-SAP_v2.0
 Author: [Redacted] Version Number: 2.0

Version Date: 29JUN2020

Template No.: CS_TP_BS016 Revision 5
 Effective Date: 01Apr2018

Reference: CS_WI_BS005

ALGORITHM FOR PRIOR / CONCOMITANT MEDICATIONS

Partial date to be imputed as:

Start date	Earliest possible date	first day of month if day unknown or 1 st January if day and month are unknown
Stop date	Latest possible date	last day of month if day unknown or 31 st December if day and month are unknown

General rules:

- If start date <= study med start date, assign as prior
- If stop date >= study med start date, assign as concomitant

[figure not shown]
If Missing Stop date: (Rule 2)

- If stop date is missing, assign as prior and concomitant

If Missing Start date: (Rule 3)

- If stop date < study med start date, assign as prior
- If stop date >= study med start date, assign as prior and concomitant

START DATE	STOP DATE	ACTION
Known	Known	General rules
	Partial	General rules
	Missing	Rule 2
Partial	Known	General rules
	Partial	General rules
	Missing	Rule 2
Missing	Known	Rule 3
	Partial	Rule 3
	Missing	Rule 2

 Document: K:\AAA\Ga-PSMA-R2\VYA27826\ Biostatistics\Documentation\SAP\v2.0\Ga-PSMA-R2-SAP_v2.0
 Author:  Version Number: 2.0

Version Date: 29JUN2020

 Template No.: CS_TP_BS016 Revision 5
 Effective Date: 01Apr2018

Reference: CS_WI_BS005

Statistical Analysis Plan

[figure not shown]

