7. SAFETY DEFINITIONS, REPORTING, AND MONITORING

7.1. Adverse Events and Serious Adverse Events

The safety of the radiolabeled imaging final product ⁶⁸Ga-PSMA-R2 will be assessed through recording, reporting and analyzing medical conditions, infections, vital signs (temperature, blood pressure, heart rate, and respiratory rate), ECGs, and safety laboratory tests (blood chemistry, hematology, urinalysis).

Adverse events encountered from the time of ICF signature through the follow-up period (until Day 28 after administration of ⁶⁸Ga-PSMA-R2) will be recorded by the Investigator on the appropriate AE pages of the eCRF as defined in the following sections. Adverse events will be recorded using the Toxicity Grading Scale for Healthy Adult and Adolescent Volunteers Enrolled in Preventive Vaccine Clinical Trials (Section 11.2).

Only adverse events with start date on or after the IP administration date will be considered treatment emergent.

After the follow-up period, the Investigator must report to the Sponsor only SAEs possibly related to ⁶⁸Ga-PSMA-R2 or to the study procedures (see SAE definition in Section 7.6.3).

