7.7. Reporting Period

Adverse Events are collected on an ongoing basis from signing of Informed Consent until the last follow up visit.

All SAEs, including deaths, independently of causality, that occur from informed consent until the last scheduled follow-up visit will be recorded on an SAE form, in addition to the eCRF data entry. After the last follow-up visit, the Investigator must report to the Sponsor only SAEs possibly related to ⁶⁸Ga-PSMA-R2 or to the study procedures.

All SAEs must be followed-up by the Investigator until resolution or stabilization, and follow-up information must be reported to the Sponsor according to the reporting procedure.

All pregnancy cases occurring one week after IP administration and until the last follow-up (Day 28) will be reported according to the SAE reporting procedures. All pregnancy reports will be followed-up until delivery.

A last batch of queries will be sent after Last Patient Last Visit for all AEs with ongoing/unknown outcomes. After the last batch of queries with all collected data have been fully processed, eCRFs and database will no longer be updated. Only SAEs and medically relevant ongoing/unknown outcome AEs will be followed-up until resolution or stabilization. Beyond this defined reporting period, any new unsolicited serious AE spontaneously reported to CRO/Sponsor by the Investigator would however be collected and processed by pharmacovigilance.

Any patient who received a partial or full dose of the investigational product and who withdraws prematurely or is withdrawn by the Investigator from the trial, should have a follow-up safety visit 28 (\pm 3) Days after the investigational product administration.

If a patient is documented as lost-to follow-up or consent withdrawal, ongoing/unknown outcome AEs will not be followed-up.

For screen failure patients, new AEs and updates must be recorded in eCRFs until the date the patient was determined to be a screen failure. Beyond that date, only SAEs possibly related to the investigational product or to the study procedures will be reported to the CRO/Sponsor.

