14.1. ADVERSE EVENTS

Adverse Events will be coded using the MedDRA central coding dictionary, Version 21.0 or higher.

They will be sorted by decreasing frequency for SOC and for PT within SOC, based on total count.

Treatment emergent adverse events (TEAEs) are defined as AEs that started or worsened in severity on or after the first and single dose of study medication and until the last actual follow up visit.

Document:	K:\AAA\Ga-PSMA-R2\VYA27826\ Biostatistics\Documentation\SAP\2.0\Ga-PSMA-R2-SAP_v2.0
Author:	 Version Number: 2.0

Template No.: CS_TP_BS016 Revision 5
 Effective Date: 01Apr2018

Version Date: 29JUN2020
 Reference: CS_WI_BS005

See Appendix 2 for handling of partial dates for AEs. In the case where it is not possible to define an AE as treatment emergent or not, the AE will be classified by the worst case; i.e. treatment emergent.

An overall summary of number of patients within each of the categories described in the sub-sections below, will be provided as specified in the templates.

Listings will include TEAEs and Non-TEAEs.

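### The SAP closes the TEAE window at the last attended visit, so an AE that starts later but within protocol follow-up is missing from the summary tables

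*SAP*

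**What the plan says.** SAP 14.1 treats an event as treatment emergent if it "started or worsened in severity on or after the first and single dose of study medication and until the last actual follow up visit". Appendix 2 turns this into an algorithm. For a known start date, whatever the stop date: "If start date < study med start date or start date > actual date of last follow up visit, then not TEAE". For a partial start date that could fall on or after dosing, with a known or partial stop date: "If start date > actual date of last follow up visit, then not TEAE". Two branches carry no upper limit: a missing start date, and a partial start date with a missing stop date. Section 14.1 adds that where emergence cannot be determined, "the AE will be classified by the worst case; i.e. treatment emergent".

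Protocol 7.1 states: "Only adverse events with start date on or after the IP administration date will be considered treatment emergent". It records AEs "from the time of ICF signature through the follow-up period (until Day 28 after administration of" the product), and then: "After the follow-up period, the Investigator must report to the Sponsor only SAEs possibly related to" the product or the study procedures. Protocol 7.7 states: "Adverse Events are collected on an ongoing basis from signing of Informed Consent until the last follow up visit". The same section records all SAEs and deaths, whatever their cause, up to the last scheduled follow-up visit.

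Protocol 8.2.1 restricts AE summaries to treatment-emergent events. SAP 14.1.1 to 14.1.4 builds the all-TEAE, discontinuation, serious and fatal tables on TEAEs. Listings include non-TEAEs.

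**The concern.** The protocol fixes its AE recording period by time since injection (7.1) and its SAE and death period by the visit schedule (7.7). The SAP fixes the TEAE window by attendance. The two part company when a patient's last attended visit falls before the end of follow-up, and an event after that visit still reaches the database.

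Two situations matter most. A patient seen on Day 7 may die, or have an SAE, before any later visit. Or a patient may discontinue, skip the 28 (±3) day safety visit of protocol 7.7, and report a new AE at the 15-day contact required by protocol 6.7, which is a contact and not a visit.

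AEs and SAEs are the primary endpoint. Followed literally, the rule lets a serious-TEAE or death table show zero when the protocol's own follow-up period contains an event.

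**Working it through.** The plan gives no figure to reproduce here, so the check applies the rule to dates.

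**Inputs**
- Dosing is Study Day 1 (SAP 6.2).
- SAP rule for a known start: TEAE if dosing ≤ start ≤ L, where L is the last actual follow-up visit (SAP 14.1, Appendix 2).
- End of protocol AE recording: E = Day 28 (protocol 7.1). With dosing as Day 1, 28 days after administration is Study Day 29, so both values are shown.
- Visits at Day 7 ± 2 and Day 28 ± 3 (protocol 6.4). Table 1 gives Day 28 (+1 day).
- Contact 15 ± 3 days after premature discontinuation (protocol 6.7).
- Planned numbers: 6 in Phase I, 12 + 12 in Phase 2, 30 in all.

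**Step 1. Onset days lost = max(0, E − L)**

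| Last actual visit (L) | Lost, E = Day 28 | Lost, E = Day 29 |
|---|---|---|
| Day 1 only (taken as the last visit) | 27 | 28 |
| Day 5 | 23 | 24 |
| Day 7 | 21 | 22 |
| Day 9 | 19 | 20 |
| Day 25 | 3 | 4 |
| Day 27 | 1 | 2 |
| Day 28 | 0 | 1 |

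The Day 25 and Day 27 rows arise only under the ±3-day window of section 6.4, not under Table 1.

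**Step 2. The 15-day contact.** For discontinuation at a Day 7 visit, contact falls on 7 + 15 = Day 22, with a range of 7 + 12 = Day 19 to 7 + 18 = Day 25. New AEs with known onset on Days 8 to 22 (15 days; 12 to 18 over the range) are excluded unless a later visit takes place.

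**Step 3. One event through Appendix 2.** Assumed dates: injection 20 March (Day 1), last visit 26 March (Day 7), AE from 3 to 8 April (Days 15 to 20).

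| Recorded start | Recorded stop | Result |
|---|---|---|
| 3 April | any | not TEAE |
| April, day unknown | 8 April | start imputed to 1 April; not TEAE |
| April, day unknown | missing | TEAE |
| missing | 8 April | TEAE |
| 3 April, Day 28 visit attended | any | TEAE |

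The first and last rows differ only in attendance. The third row is an internal inconsistency: every April date lies after 26 March, yet no upper limit applies.

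For partial starts the cut-off operates only outside the month (or, if only the year is known, the year) of dosing. Inside it, the start is imputed to the dosing date.

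**Step 4. Scale of one excluded patient**, assuming the patient would otherwise count in that table row:
- Overall: 1/30 = 3.3%. The table would show 0/30 (exact 95% CI 0 to 11.6%) instead of 1/30 (0.1 to 17.2%).
- PCa-BR: 1/18 = 5.6%.
- mPCa, or Phase II PCa-BR: 1/12 = 8.3%. The table would show 0/12 (0 to 26.5%) instead of 1/12 (0.2 to 38.5%).
- Phase I PCa-BR, presented separately under SAP 6.1: 1/6 = 16.7%.

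**The case against.** **Protocol 7.1 does not define every later AE as treatment emergent.** A reader might infer that any AE starting after injection is treatment emergent under the protocol, so that any upper limit in the SAP contradicts it. The text does not support that. It says only events on or after administration qualify, which is a necessary condition and a lower bound. Protocol 8.2 leaves analysis detail to the SAP. An upper limit is legitimate; the difficulty is where this one sits relative to the recording period.

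**The SAP wording has a source.** Protocol 7.7 collects AEs until the last follow-up visit. This stands in part. But that sentence governs collection, does not say whether the visit is actual or scheduled, differs from 7.1, and is accompanied by a rule that takes SAEs and deaths to the last scheduled visit.

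**Appendix 2 could mean something milder.** Its phrase could denote the actual, as opposed to nominal, date of the final visit. Section 14.1 speaks of the last actual visit, which favours the attendance reading. On the milder reading, a patient who never attended Day 28 has no cut-off date at all, so clarification is still needed.

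**The worst-case principle is mostly respected.** A reader might infer that the SAP contradicts it by counting a missing start date and excluding a known one. It does not: a missing start is doubtful and takes the worst case as promised, while a known late date is not doubtful. Only the partial-start, missing-stop branch is out of line.

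**Few patients will be affected.** This is conceded. The 28 (±3) day visit covers many withdrawals, AEs are obtained at scheduled visits (7.6.1), and entry requires ECOG 0-2 and life expectancy of at least 6 months. For a completer seen up to 3 days early, the effect is small.

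**Conclusion.** The point holds. As written, the SAP excludes from every TEAE-based table an AE that starts after the last attended visit but within protocol follow-up. This applies to known starts, and to partial starts imputed after that visit when the stop date is known or partial. Up to 21 onset days are lost for a patient last seen on Day 7, taking Day 28 as Study Day 28.

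The number of patients affected cannot be derived, because the documents give no dropout, death or AE rate. The percentages above are for scale and are not forecasts. The harm is confined to summary tables, since AEs, SAEs and fatal AEs all remain listed. Even so, those tables report the primary endpoint, and a listing does not correct a zero in an incidence table. It should be fixed.

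The conclusion rests on reading the cut-off as the last attended visit, as section 14.1 words it, and on the late event having reached the database.

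**What to change.** - In SAP 14.1, and in the known-start and partial-start branches of Appendix 2 that carry the limit, replace the cut-off with the later of (a) the end of the protocol follow-up period and (b) the actual final visit, whether or not the Day 28 visit was attended.
- State (a) as a Study Day consistent with SAP 6.2. If 28 days after administration is meant, that is Study Day 29.
- Reconcile the AE recording period in protocol 7.1 with protocol 7.7, and the Day 28 visit window in Table 1 (+1 day) with section 6.4 (±3 days).
- Report possibly related SAEs that start after the window separately. Removing the upper limit altogether would mix complete AE collection with events reported selectively after follow-up.
- State whether the partial-start, missing-stop branch is meant to have no upper limit.

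The cost is SAP text and one derivation, with no new data. Changing the cut-off can only leave TEAE counts the same or raise them. Adding a limit to the partial-start, missing-stop branch could lower them, so that is a separate decision.

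### SAP Appendix 2 counts an adverse event as treatment-emergent when its own dates show it ended before injection: year-only start in the dosing year, partial stop in an earlier month

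*SAP*

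**What the plan says.** SAP 14.1 defines TEAEs as "AEs that started or worsened in severity on or after the first and single dose of study medication", up to the last follow-up visit. Its worst-case default to treatment-emergent applies only "In the case where it is not possible to define an AE as treatment emergent or not". Protocol 7.1 is narrower: "Only adverse events with start date on or after the IP administration date will be considered treatment emergent".

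Appendix 2 turns this into a table for incomplete dates. The relevant rows concern a partial start that could fall on or after dosing.

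- **Start imputation.** The start becomes its earliest possible date. The exception is a start that shares the dosing month and year, or the dosing year when only the year is known: "In the latter cases, the study med start date will be used for the imputation".
- **Partial start, known stop.** If the imputed start is after the stop: "Consider the start date as Missing and apply the algorithms for missing start date". The stop is kept.
- **Partial start, partial stop.** The stop rule is "Impute stop date as latest possible date". If the imputed start is after the imputed stop: "Consider the start and stop dates as Missing and apply the algorithms for missing start date". The stop is discarded.
- **Missing start, known or partial stop.** "If stop date < study med start date, then not TEAE".
- **Both missing.** The event is assumed treatment-emergent.

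**The concern.** The partial/partial row throws away the one piece of information that settles the question. If the latest date on which an event could have stopped is before injection, the event can neither have started nor have worsened after injection. It fails both the SAP and the protocol definition. Its status is known, so the worst-case default does not apply.

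The table is also inconsistent with itself. With the start wholly missing, the same partial stop gives not treatment-emergent. Adding the start year, which is more information and does not conflict with the stop, reverses that to treatment-emergent.

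Adverse events are part of the primary safety endpoint (Protocol 2.2.1, SAP 14), and Protocol 8.2.1 restricts the AE summaries to treatment-emergent events. A screening event that ended before injection would therefore enter those tables. SAP 6.1 presents PCa-BR separately by phase, so single patients carry visible weight.

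**Working it through.** The plan gives no figure to reproduce. The check traces the rules and then asks how often the dates can meet the condition.

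**1. One event through three rows.** Assumed dosing date 10 June 2019.

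| Recorded start | Recorded stop | Path | Result |
|---|---|---|---|
| 2019 | 31 May 2019 | Start imputed to 10 June, after the stop; start set to missing; stop before dosing | Not TEAE |
| Missing | May 2019 | Stop imputed to 31 May; before dosing | Not TEAE |
| 2019 | May 2019 | Start imputed to 10 June, stop to 31 May; start after stop; both set to missing | TEAE |

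The recorded dates in the third line do not conflict: an onset somewhere in 2019 is compatible with a stop in May 2019. The reversal comes only from imputing the start to the dosing date.

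**2. The row's own safeguard cannot operate.** The partial/partial row contains the line "If stop date < study med start date, then not TEAE", but only under the condition that imputed start is on or before imputed stop. In this row the imputed start is either the dosing date or the first day of a later month or year, so it is never before dosing. If start ≤ stop and start ≥ dosing, then stop ≥ dosing, and the line is never reached.

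**3. All date patterns.** The table was applied to every dosing date in an illustrative year (2019), with every month-and-year or year-only start and stop in 2018 to 2020, keeping starts that could be on or after dosing.

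- Combinations examined: 291,447. The safeguard line was reached in 0.
- Latest possible stop before dosing: 134,106. The partial/partial row gives TEAE in all of them; the partial/known and missing/partial rows give not TEAE in all of them.
- Internally consistent as recorded: 2,017, or 2,017/134,106 = 1.5%. All have a year-only start in the dosing year.
- Recorded start after recorded stop: 134,106 − 2,017 = 132,089.

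The 2,017 can be checked by hand. A dosing date in calendar month M has M − 1 earlier months of that year available as a stop month. Summing days in the month × (M − 1) over 2019 gives 0 + 28 + 62 + 90 + 124 + 150 + 186 + 217 + 240 + 279 + 300 + 341 = 2,017. These counts are date patterns, not expected event frequencies.

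**4. When a screening event can qualify.** AEs are recorded from consent (Protocol 7.1) and screening runs from Day -14 to Day -1 (Protocol 6.2). The stop must fall in an earlier month of the dosing year. If all 14 days are used, dosing must fall on day 1 to 14 of February to December: 11 × 14 = 154 dates, and 154/365 = 42%. January dosing cannot qualify, because the earlier month lies in the previous year.

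**5. Effect of one misclassified patient with no other TEAE.** Overall 1/30 = 3.3 percentage points; a Phase 2 group 1/12 = 8.3; Phase 1 1/6 = 16.7. Denominators are the planned numbers in the protocol synopsis.

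**The case against.** The best defence is that the branch mostly catches bad data. It fires whenever the imputed start is after the imputed stop, and 98.5% of the date patterns above with a stop before dosing have a recorded start later than the recorded stop. There the two dates contradict each other, the stop proves nothing, and a worst-case default is reasonable. This stands, and it limits both the finding and the remedy. With dosing on 10 June 2019, start July 2019 and stop May 2019, keeping the stop would remove an event recorded as starting after dosing.

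Practical reach is also very small. A site would have to know the month in which an event stopped but not the month in which it began, for an event that arose after consent and ended before dosing. eCRF pages are due within 5 working days and queries must be answered within 5 (Protocol 8.5). The error over-counts, no formal testing is planned (SAP 6.6), and all events are listed, with imputed dates not shown. That stands too.

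Nor do all nearby rows disagree: partial start with missing stop also gives treatment-emergent. There, however, no stop date exists to say otherwise.

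A reader might infer three stronger things that the documents do not support.

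- *Every event reaching this branch is misclassified.* Only the consistent date patterns are.
- *Affected events would also be counted as drug-related.* SAP 14.1.1.2 does treat missing causality as related, but nothing links incomplete dates to missing causality, and Protocol 7.6.2 asks for causality in every report.
- *TEAE incidence is itself the named primary endpoint.* The endpoints are AEs and SAEs plus laboratory, vital-sign and ECG changes; TEAE status decides which events enter the AE summaries.

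**Conclusion.** The rule is wrong as written for one narrow pattern: a year-only start in the dosing year with a partial stop in an earlier month of that year. Such an event is labelled treatment-emergent although its dates show that it ended before injection. Neither TEAE definition nor the worst-case default covers it, and two rows of the same table give the opposite answer. The unreachable safeguard line suggests that the intention was to exclude such events.

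This is a minor specification error, rare and conservative. The 42% assumes that every patient uses the full 14 days and that dosing dates are spread evenly over the year. It describes the calendar and includes no probability of a screening event or of a year-only start, for which the documents give no figures. The percentage-point effects on TEAE incidence assume that the patient has no other TEAE and that planned enrolment is met.

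**What to change.** In the partial start / partial stop row of SAP Appendix 2, split the branch where the imputed start is after the imputed stop:

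1. If the recorded components are consistent (recorded start not after recorded stop) and the latest possible stop is before the study medication date, treat only the start as missing, keep the imputed stop and apply the missing start / partial stop row. The event is then not treatment-emergent.
2. If the recorded start is after the recorded stop, query the dates. If the query does not resolve them, keep the present default to treatment-emergent.

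The condition in step 1 should not be dropped: without it, an event recorded as starting after dosing could leave the summaries. Events whose stop could be on or after dosing are unaffected. The cost is a short edit to one cell of the table and the matching condition in the program; no new data are needed.

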12. CANCER THERAPIES, MEDICATIONS, PROCEDURES AND RADIOTHERAPY

12.1. PRIOR AND CONCOMITANT CANCER THERAPIES

Prior and concomitant cancer therapies, as reported in the “Prior and Concomitant Cancer Therapy Medications” eCRF page, will be presented for the FAS and PPS using WHO-DD Preferred Names.

- Prior cancer therapies are those which started prior to the day of first and single dose of study medication.
- Concomitant cancer therapies are those which:
 - started prior to, on or after the first and single dose of study medication, AND
 - ended on or after the date of first and single dose of study medication or were ongoing at the end of the study.

Number of patients with at least one Line of therapy (Neoadjuvant, Adjuvant, Therapeutic for Metastatic Disease, Unknown), number of patients with at least one Therapy type (Chemotherapy, Hormonal, Biological, Immunotherapy, Other), number of patients with at least one Treatment intent (Curative, Palliative, Diagnostic, Salvage, Other) will be presented as well as the medication and the best response of the latest therapy the patient received (Complete response, partial response, stable disease, progressive disease, not evaluable).

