12.4. PRIOR AND CONCOMITANT RADIOTHERAPY

Prior and concomitant radiotherapy, using radiation type as reported in the eCRF, will be presented by radiation type and treatment intent. The total dose received (Gray) will also be summarized. See APPENDIX 2 for handling of partial dates for prior and concomitant radiotherapies. In the case where it will not be possible to define a radiotherapy as previous or active/concomitant.

- Prior radiotherapies are defined as those which started prior to the first and single dose of study medication.
- Concomitant radiotherapies are defined as those which:
 - started prior to the first and single dose of study medication and are ongoing or active at the date of the first and single dose of study medication
OR
 - started on or after the first and single dose of study medication.

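### SAP Appendix 2 does not reproduce the plan's own definitions of prior and concomitant treatment, in three respects

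*SAP*

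**What the plan says.** The body of the SAP defines the categories. In 12.1, "Prior cancer therapies are those which started prior to the day of first and single dose of study medication"; concomitant therapies are those that "ended on or after the date of first and single dose of study medication or were ongoing at the end of the study". Section 12.2 uses the same two definitions for non-cancer medications. Section 12.4 makes radiotherapy that starts on or after the dose concomitant, with no condition on its stop date. Protocol 7.4 counts medication taken from Day 1 onward as concomitant, and SAP 6.3 treats medications starting on the reference date as post-baseline.

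Appendix 2 then gives two algorithms. One is headed "ALGORITHM FOR PRIOR / ACTIVE PROCEDURES, RADIOTHERAPIES, CANCER THERAPIES AND MEDICATIONS", the other "ALGORITHM FOR PRIOR / CONCOMITANT MEDICATIONS", so medications fall under both. Each has a General rule for prior, "If start date <= study med start date, assign as prior", and a General rule for concomitant that needs a stop date on or after dosing. Each also has a separate missing-stop rule, "If stop date is missing, assign as prior and concomitant" (Rules 2 in the first, Rule 2 in the second). For a known start, the first algorithm's table reads "Missing General rules"; the second calls Rule 2 in the same cell.

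Section 12.2 has a worst-case fallback to concomitant. In 12.4 the corresponding sentence stops before its main clause: "In the case where it will not be possible to define a radiotherapy as previous or active/concomitant". Section 12.3 has the same unfinished sentence, and 12.1 has no fallback.

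**The concern.** A complete start date with no stop date is the usual form of a record for continuing treatment, and it is where the two algorithms part. Continuing treatment of this kind is foreseeable: protocol 5.6 exempts LHRH/GnRH from its restriction on cancer therapy, and cancer therapies are recorded through the end of the study. The dosing-day boundary also matters in a single-injection safety study, because anything given after the injection on Day 1 falls on it. Two programmers working from this SAP could produce different prior and concomitant tables, and neither set would match Section 12 throughout.

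**Working it through.** There is no sample-size or power figure to reproduce. The check is to run typical records through the printed rules and compare the labels.

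Write D for the dosing date, S for start, E for stop.

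- General rules (both algorithms): prior if S ≤ D; concomitant if E ≥ D. A missing E is taken not to meet E ≥ D.
- Rules 2 / Rule 2 (missing E): prior and concomitant, whatever S is.
- Rules 3 / Rule 3 (missing S): prior if E < D; prior and concomitant if E ≥ D.
- SAP 12.1 and 12.2: prior if S < D; concomitant if E ≥ D or the treatment is ongoing at the end of the study.

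Each table has nine cells (start known, partial or missing, by stop known, partial or missing). The two tables differ in one of the nine: known start, missing stop.

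| Start | Stop | First algorithm, by its table | Second algorithm | SAP 12.1/12.2 |
|---|---|---|---|---|
| Before D | None | Prior | Prior + concomitant | Prior + concomitant |
| On D | None | Prior | Prior + concomitant | Concomitant |
| After D | None | No label | Prior + concomitant | Concomitant |
| Before D | Before D | Prior | Prior | Prior |
| Before D | After D | Prior + concomitant | Prior + concomitant | Prior + concomitant |
| On D | After D | Prior + concomitant | Prior + concomitant | Concomitant |
| After D | After D | Concomitant | Concomitant | Concomitant |
| Day unknown, month of D, truly after D | After D | Prior + concomitant | Prior + concomitant | Concomitant |

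In the last column a record with no stop date is read as ongoing. In the last row the start is imputed to the first of the month, which puts it on or before D.

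The table shows three separate faults.

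(a) *Rows 1 to 3, first algorithm.* The cell conflicts with that algorithm's own Rules 2 and with the second algorithm. By the cell, a treatment begun before dosing loses its concomitant label and one begun after dosing has no label.

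(b) *Rows 2 and 6, both algorithms.* The ≤ sign adds prior to a treatment begun on the dosing day. The concomitant label is normally kept; it is lost only in row 2 under the first algorithm's cell.

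(c) *Row 3, second algorithm.* Rule 2 ignores the start date, so a drug known to have begun after dosing is labelled prior as well as concomitant. Following Rules 2 instead of the cell in the first algorithm gives the same result.

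Choosing one printed algorithm over the other therefore does not restore agreement with Section 12.

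**The case against.** The best defence has four parts.

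First, the first algorithm contains its own missing-stop rule, stated without conditions, and the conflicting table cell may be a slip. Second, Appendix 2 is titled as a partial-date convention, 12.2 to 12.4 cite it for that purpose, and 12.1 does not cite it at all. A known start with an ongoing record can be classified from 12.1 directly, and post-dose radiotherapy from 12.4 directly. Third, the documents never say that an ongoing record is one with a missing stop date. Fourth, the outputs are descriptive, there is no formal testing, and prior and concomitant treatment is not an endpoint.

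Much of this stands, and it rules out two stronger readings. A reader might infer that continuing cancer therapy will vanish from the concomitant table. That needs the cell to override both Rules 2 and 12.1, ongoing to be coded as a missing stop, and a complete start date; a partial or missing start with a missing stop goes to Rules 2 and stays concomitant. Castration type is also summarised separately under SAP 11.2. A reader might likewise infer that a drug given for a reaction to the injection would be shown as pre-existing. Under the medication algorithm it is labelled prior and concomitant, so it stays in the concomitant table with one label too many.

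The defence does not remove the defect. Both tables include rows for fully known dates, so they act as complete classification rules. A slip in a cell is still an instruction to a programmer, and faults (b) and (c) do not depend on it.

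**Conclusion.** The point holds as a conflict between Appendix 2 and the definitions it should implement: one table cell of nine in the first algorithm, the ≤ sign in both, and the missing-stop rule when the start is known to be after dosing. Records with a known start after dosing and a known stop are classified correctly.

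The effect is limited to the descriptive tables of prior and concomitant treatment. Treatment-emergent status has its own date algorithm in Appendix 2, so those counts and the other primary safety summaries do not change. No number of patients can be given: it depends on how many records have a complete start date and no stop date, how many treatments began on the dosing day, and whether ongoing is handled as a missing stop. The missing figures beside the General rules were not counted against the plan. The correction should be made before the tables are programmed.

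**What to change.** Replace the two algorithms with one for all treatment types:

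- Prior: known or imputed start < dosing date.
- Concomitant: stop ≥ dosing date, or stop missing or ongoing. State that ongoing is handled this way.
- Known start on or after the dosing date: concomitant only, whatever the stop date.
- Known start before dosing with a missing or ongoing stop: prior and concomitant.
- Wholly missing start: keep Rule 3 when a stop date is available, and Rule 2 when the stop is missing too. Without Rule 3, a missing start with a pre-dose stop would get no label.
- Partial start that could fall on or after dosing: state one rule consistent with the 12.2 worst case, that is, concomitant, unless the stop date shows the treatment ended before dosing.

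Complete the unfinished sentences in 12.3 and 12.4 with the same fallback, and add it to 12.1. The eCRF pages are not shown; if one-off procedures are recorded with a single date, say that this date also serves as the stop, so that past surgery is not made concomitant by the missing-stop rule.

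The cost is SAP wording and one programming rule. No new data are needed.
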